13.1 Identification of potential study participants

Study participants can be identified by either of two methods:

- Identification by the trial site personnel, from among the site's MA patients
- Online pre-screening

13.1.1 Identification by trial sites

Trial sites will be allowed to contact its MA patients, informing them about the study and inquiring about their interest in participating. The trial site personnel are allowed to contact such individuals via letter, telephone or in the clinic.

The sponsor will supply trial sites with informational brochures and/or posters about the study, for placing in relevant locations at the site (e.g. in waiting rooms), cf. the documents **PAREMA1** *information flyer* and **PAREMA1** *advertisement*.

13.1.2 Online automatic pre-screening

This recruitment will be organized by the sponsor and will focus on areas near study sites.

Online and physical advertisements of the study will include a link to a pre-screening website with an online eligibility questionnaire to be completed by the potential participant before being invited to the study site for the screening/inclusion visit (Site Visit 1), cf. the document **PAREMA1 Case Report Form content**. This pre-screening step aims to reduce the screen failure rate of the on-site visits. Before completing the pre-screening survey, the potential participant will be provided with a privacy statement and required to provide consent to being contacted by trial site personnel.

If the individual's answers in the online pre-screening conform to the in/exclusion criteria, they will receive the Informed Consent Form for their perusal, as well as the telephone number to the study site, and they will be asked to call in order to book a time for the Site Visit 1. The potential participant will in this process be required to provide their telephone number and email so that the study site has the option of contacting the patient.

The pre-screening website will be hosted by the sponsor on a secure server, and the telephone numbers and emails will be handled confidentially and in accordance with local and national data protection rules.

When the visit has been booked and entered in the study site's calendar, the potential participant will receive an email with information about the study and Site Visit 1. A text message and email reminder will also be sent to the patient 24 hours prior to the site visit.

13.2 Site Visit 1

13.2.1 Informed Consent

The potential participant is briefed by the PI or delegated study personnel (hereafter designated PI) about the study, including the study rationale, study plan, randomization to either study device or sham device, study design and possible side effects of the treatment. It is clearly explained to the patient that they may be assigned to either a functional (active) or non-functional (sham) device in Stage 1, that it is believed that the active device has the best treatment effect and that the participant is guaranteed to be assigned to this in Stage 2.

If the participant wishes, he/she can have up to a week to consider before deciding whether or not to participate (in that case, the visit will be stopped after Step 1 and resumed when the participant has decided).

A potential study participant considered for this study must be listed on a screening log to be maintained at the site. The PI must also enter in the participant's medical records that he/she is participating in the study. If the participant does not have a medical record at the study site, a new record must be started for him/her.

PI will instruct female participants of childbearing potential to practice effective contraception during their participation in the study.

13.2.2 Information to be recorded:

The following information is obtained and documented in the eCRF during Site Visit 1 (cf. document **PAREMA1 Case Report Form content**):

- General eligibility questions (e.g. age, headache frequency, current participation in other clinical investigations)
- Eligibility questions related to migraine with aura diagnosis (presence of aura symptoms, frequency of MA attacks, age at MA onset)
- Eligibility questions related to headache drug use and overuse
- Eligibility questions related to comorbidities (e.g. pulmonary, cardiovascular and cerebrovascular disease)
- Eligibility questions related to secondary headaches (e.g. caused by head/neck trauma or infection)
- Pulse oximeter test result (see section 13.2.3)
- Capillary blood test for anaemia
- For female patients:
 - Whether the patient has gone through menopause
 - \circ $\;$ If patient has not gone through menopause: urine pregnancy test $\;$
- Other eligibility questions, including participant's willingness to abide by study instructions, and ability and willingness to provide informed consent.
- Migraine without aura (MO) diagnosis and frequency
- Miscellaneous baseline information (e.g. self reported height and weight, ethnicity, Most Bothersome Symptom during MA attacks, currently and previously used migraine drugs, questions regarding efficacy of current acute treatment, evaluation of depression, anxiety and stress via the DASS-21 (Depression Anxiety Stress Scales 21 item questionnaire))

13.2.3 Pulse oximeter test

The oxygen saturation (S_{pO2}) of the participant is measured with the pulse oximeter (see section 8.7). Initially, the study personnel should check whether the participant is wearing nail polish and/or false nails. In that case, the pulse oximeter finger probe must be placed on the finger at a 90 degree angle to avoid measurement inaccuracies.

The S_{pO2} measurement should be performed at baseline, after the participant has relaxed in a chair for one minute. The study personnel must enter the S_{pO2} reading at the one minute time point into the eCRF. The study personnel should during the one minute conduct small talk with the participant in order to make them relax and breathe normally, in order to avoid as much as possible that white coat

syndrome biases the reading. If the baseline S_{pO2} reading is lower than 95%, the patient is ineligible for the study.

13.2.4 Point of enrolment

A participant is considered finally enrolled at the time the informed consent form (ICF) is signed and all eligibility criteria are met. The PI is responsible for the selection and screening process at the site and will document eligibility in electronic CRF (eCRF). No study related tests or procedures will take place before informed consent is obtained. All participants that are successfully enrolled will be documented on the enrolment log. Participants not meeting eligibility criteria after having signed the ICF are considered screen failures and documented on the screening log. The reason for screen failure must also be documented. Excluded participants will at this point be informed about other treatment options. Screen failures are not included in the intended sample size. Screen failures may be enrolled at a later stage, if by then eligibility can be met. Participants can only be enrolled and participate in the study once.

13.2.5 General data capture

The participant will receive an email via the EDC system, with a link to download the ePRO app (iOS or Android), and with their unique Participant Identification Number (PIN) which is generated by the EDC system and is used as access code when entering data in the ePRO app.

At this point the PI must help the participant install the ePRO app on their smartphone. This includes:

- Setting up automatic login to the ePRO app via either thumb or face recognition (according to the participant's preference) provided that this type of login is possible on the user's specific smartphone
- Turning on notifications for the Trialkit app, with all available types of notifications turned on (sounds, banners, popup messages and others).

13.2.6 Finalization of Site Visit 1

The participant receives their study device kit, which contains:

- Five study/sham devices. The Attack Checklist (cf. section 13.4.1) is printed on each device's packaging.
- PAREMA1 Instructions for Use (active or sham type as appropriate)
- Label on the study device kit's lid including the Study Kit Identifying Code (cf. Investigator's Brochure)

The participant's PIN is at this point written on the designated space on the packaging of all study devices, as well as on the study device kit's label.

The PI and participant then schedule the participant's at-home Instruction Session that takes place at home via teleconference between an instructor from the CRO and the participant (see section 13.3 below). The Instruction Session must be scheduled as soon as possible after Site Visit 1 (maximum one week later).

13.2.7 Summary of tasks during Site Visit 1:

 Table 3: Tasks during Site Visit 1

TASKS, Site Visit 1:		
1.	Inform the participant about the study, including the study rationale, study plan and possible side	
	effects of the treatment.	
2.	Participant signs informed consent form	
3.	General eligibility questions	
4.	Pulse oximeter test	
5.	Anaemia test	
6.	For female participants: Pregnancy test	
7.	Decision on eligibility for study according to checklist and investigator's evaluation	
8.	Randomization	
9.	Install ePRO study app on subject's smartphone	
10.	Patient receives study device kit and Instruction Session is scheduled	

13.3 Instruction Session

In order to preserve the blinding of the investigator, the participant training and device configuration are performed via teleconference by a Contract Research Organization instructor. This Instruction Session takes place via teleconference and covers configuring and using the study device, reporting data via the ePRO app, and safety reporting.

The instruction session has five parts (for details refer to the document **PAREMA1 Case Report Form Content**)

- 1. **Initial briefing of the participant**. This entails explaining the aims of the instruction session and what will happen during it. The participant is encouraged to ask any questions they have.
- 2. **Briefing on essential steps when an aura begins**. The instructor explains the steps the participant must follow when an aura begins, as described in Part 3 of the Instructions for Use and summarized in the Attack Checklist printed on the device packaging.
- 3. Using the study device for the first time. The participant follows the steps described in Part 1 of the IfU, in order to learn how to use the device and to find the optimal regulator setting. The instructor corrects any errors. Afterwards, the participant is instructed to write their optimal regulator setting on each of the attack checklists on the device packages.
- 4. Learning how to report symptoms in the Trialkit app. The participant follows the steps described in Part 2 of the IfU, in order to learn how to correctly report symptoms in the app. The instructor checks that the attack is correctly reported and registered in the EDC, and corrects any errors.
- Final instructions and reminders. The participant describes the essential attack instructions in their own words to the instructor, and any errors are corrected. In addition, a number of general instructions and reminders are given to the participant (cf. PAREMA1 Case Report Form Content)

13.4 Stage 1

In Stage 1 of the study, the participants will treat up to four attacks each, all of which with either the active or sham device. The treatment is started at the onset of aura symptoms and continues until the aura symptoms have disappeared, or until 120 minutes have passed, whichever occurs first. At that point, the participant turns the slider to position 1 and breathes through the device for five more minutes³. Due to the nature and normal duration of aura, and the in/exclusion criteria related to aura, the great majority of participants will use the device for less than an hour. As an added control mechanism, the eCRF study app asks participants if they are still using the device at the 2-hour time point; if this is confirmed the participant is directed to stop using the device at that point.

The first treated attack is designated a *training attack* and will not be used in the statistical analysis. The subsequent treated attacks are designated *study attacks* and will be used in the statistical analysis.

After four treated attacks or overall conclusion of Stage 1 (whichever comes first), participants will end study Stage 1 and have the option to start Stage 2 which is a follow-up open-label period during which the participant will treat up to five attacks with the active device type.

13.4.1 Stage 1 At-Home Activities

Participants are instructed to have a study device and the ePRO app at hand at all times, and at the onset of aura symptoms follow the Attack Checklist (see section 13.4.1.1) to start the treatment and the logging of the attack in the ePRO app.

In the following cases, the participant should NOT treat the attack with the study device or record it in the study diary app:

- 1) If there are no aura symptoms (these are pre-specified in the Instructions for Use and ICF)
- 2) If there is moderate or severe headache at the time the aura symptoms start
- 3) If they are not able to start treatment within 10 minutes of beginning of the aura symptoms

The start of treatment is counted as time point 0.

Data are collected via the ePRO app at specified time points (0, 1, 2, 24 and 48 hours). If the app is not available (e.g. internet connection issues), the patient should report the data in paper forms provided during Site Visit 1.

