10.2 Hypothesis

It is the primary hypothesis of the study that early treatment with the Rehaler device increases the likelihood of having no or only mild headache two hours after starting the treatment, compared with a sham device. "Early treatment" is here defined as treatment that is initiated during the aura phase, within ten minutes of aura symptoms onset, and before the start of moderate or severe migraine

headache. The primary endpoint is the absence of moderate or severe pain at 2 hours (AMSP2) after early treatment.

The primary effectiveness hypotheses are:

H₀: p_{Rehaler} = p_{sham} (null hypothesis)

 $H_a: p_{Rehaler} \neq p_{sham}$ (alternative hypothesis)

Where:

p_{Rehaler} = proportion of attacks in the Rehaler group with AMSP2

p_{sham} = proportion of attacks in the sham group with AMSP2

The primary effectiveness hypothesis will be tested using a two-sided adjusted χ^2 test for clustered binary data developed by Donner and Banting (Donner and Banting, 1988), with a 5% level of significance.

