16.1 Primary Effectiveness Analysis

The primary endpoint is Absence of Moderate or Severe pain at 2 hours (AMSP2), i.e. the percentage of study attacks in which the participant reported absence of headache of moderate/severe intensity at 2 hours post-treatment initiation. "Study attacks" are all attacks treated and reported during Stage 1, apart from the first attack which is a training attack and is not included in the analysis. The intention-to-treat (ITT) analysis set will be used for the primary effectiveness hypothesis test. The primary effectiveness hypothesis is:

H₀: $p_{Rehaler} = p_{sham}$ H_a: $p_{Rehaler} \neq p_{sham}$ Where: $p_{Rehaler} = proportion of attacks in the Rehaler group with AMSP2$ $p_{sham} = proportion of attacks in the sham group with AMSP2$

The primary effectiveness hypothesis will be tested using a two-sided adjusted χ^2 test for clustered binary data (Donner and Banting, 1988), at a 5% level of significance. If Pearson's chi-squared test statistic is written as $\chi^2 = \sum_{i=1}^{G} \chi_i^2$ with G = the number of treatment groups, then the adjusted χ^2 approximately follows a chi-squared distribution with G-1 degrees of freedom and is calculated as follows (Donner and Banting, 1988):

$$\chi_A^2 = \sum_{i=1}^G \frac{\chi_i^2}{\overline{C}_i}$$

Where:

$$\overline{C}_{i} = \sum_{j=1}^{n_{i}} \frac{m_{ij}C_{ij}}{\sum m_{ij}}$$

 $C_{ij} = 1 + (m_{ij} - 1)\rho$

G is the number of treatment groups

 $n_{i}\xspace$ is the number of individuals in group j

 $\boldsymbol{\rho}$ is the correlation coefficient between any two responses in the same individual

m_{ij} denotes the number of observations for individual j in group i

The corresponding 95% confidence interval for the difference in proportion of attacks with AMSP2 between the Rehaler and sham groups will be calculated as follows (Donner and Klar, 1993):

95% Confidence Interval: $(\hat{p}_{Rehaler} - \hat{p}_{sham}) \pm 1.96 * \widehat{SE}(\hat{p}_{Rehaler} - \hat{p}_{sham})$

Where:

 $\hat{p}_{Rehaler}$ = observed proportion of attacks in the Rehaler group with AMSP2

 \hat{p}_{sham} = observed proportion of attacks in the sham group with AMSP2

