#### 1.6 Analysis sets

#### 1.6.1 Intention-to-treat (ITT) analysis set

The ITT includes all study attacks from all participants who underwent randomization and who reported at least one study attack. The ITT analysis set will not exclude attacks with protocol deviations or use of rescue medication before the two-hour time point. The ITT data set will be used for analysis of the primary and secondary effectiveness end points.

If any subjects in the ITT population have a missing headache score at the two-hour time point, multiple imputation may be used to impute their headache score for the analysis of primary and secondary endpoints, as described in section 1.9.

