#### 1.6.3 Per-protocol analysis set

The per-protocol analysis set includes all study attacks with a reported headache score at the twohour time point, in which:

- The participant started using the study device within five minutes of the beginning of aura and before development of moderate or severe pain
- The participant did not use rescue drugs before the two-hour assessment point
- There were no changes in concomitant preventive treatment during the study that might potentially affect response.
- There were no other major protocol deviations

When comparing the ITT and Per Protocol analysis sets, the impact of protocol deviations and user errors can be investigated with the aim of identifying potential improvements to the investigational device and instructions for use. The ITT analysis set will also be used to analyse the impact of protocol deviations on the outcome parameters (e.g. use of rescue medication during the first two hours and starting the use of the device after the onset of headache).

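### Protocol 13.4.1 tells a participant who uses the device in a barred attack not to record it, so such attacks would be missing from the ITT set with number and arm unknown

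*Protocol*

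**What the plan says.** **At-home rule.** Protocol 13.4.1 gives three situations in which "the participant should NOT treat the attack with the study device or record it in the study diary app". One is the absence of aura symptoms. The other two matter here: "If there is moderate or severe headache at the time the aura symptoms start" and "If they are not able to start treatment within 10 minutes of beginning of the aura symptoms".

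**Primary hypothesis.** Protocol 10.2 limits the hypothesis to early treatment, meaning "treatment that is initiated during the aura phase, within ten minutes of aura symptoms onset, and before the start of moderate or severe migraine"; the last condition refers to pain.

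**Unit of analysis.** Under Protocol 16.1, study attacks "are all attacks treated and reported during Stage 1, apart from the first attack which is a training attack". SAP 1.7.1 says the same. Protocol 13.4 calls the treated attacks after the first one study attacks, without adding that they must be reported.

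**ITT set.** SAP 1.6.1 states: "The ITT analysis set will not exclude attacks with protocol deviations or use of rescue medication before the two-hour time point". Protocol 16.8.1 agrees. SAP 1.6.3 adds: "The ITT analysis set will also be used to analyse the impact of protocol deviations on the outcome parameters", and gives early rescue and starting the device after headache onset as examples. Protocol 16.8.3 repeats this.

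**Attack Checklist.** Protocol 13.4.1.1, printed on each device package (13.2.6), has the participant start breathing at step 7 and open the app to register the attack at step 8. It lists no exception for delay or pain.

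**The concern.** Section 13.4.1 joins two instructions in one sentence: do not treat, and do not record. The first selects which attacks qualify. The second matters only when the first has been broken, and then it works against the analysis plan. A device use outside the conditions is the kind of deviation that the ITT set is said to keep, yet the participant is told to leave it out of the only system that would show it.

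The decision is made at home, after randomisation, by someone who has already used the assigned device in the Instruction Session (Protocol 13.3) and usually in a training attack. The active device can cause noticeable effects such as deeper or faster breathing (14.1.1). The tendency to leave an attack unrecorded could therefore differ by arm, and the planned data would not reveal it.

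The planned correlations of AMSP2 and PF2 with treatment delay and with pain at treatment start (Protocol 11.4.1, items 14 and 15) would also lose part of their range.

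**Working it through.** The plan gives no figure for such attacks, so the check is mainly a comparison of texts.

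1. **Participant obeys 13.4.1.** The attack is neither treated nor recorded. It is not a deviation, and it is not a study attack under 16.1. Nothing conflicts with ITT. However, no Stage 1 log of such auras is described, so their number by arm is unknown.

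2. **Participant treats despite the bar and records.** The attack enters ITT as a deviation, as SAP 1.6.1 intends. Delay and pain are asked at the start (Protocol 13.10.4 and 13.10.2), so it can be identified.

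3. **Participant treats despite the bar and follows the recording half of the sentence.** The attack never reaches the database. It would be a study attack under 13.4 but not under 16.1. The checklist would have had this participant open the app, so two participant-facing rules disagree. No section says that a device use in breach of the conditions must still be recorded.

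4. **Can later analyses recover case 3?** No. The imputation and tipping-point analysis in SAP 1.9 deal with missing outcomes, and imputation is confined to study attacks in the ITT population. An attack that was never entered is not a missing outcome.

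5. **Which deviations still reach ITT?** Rescue before two hours; starts between five and ten minutes, which fall outside the per-protocol window but inside 13.4.1; moderate or severe pain arising between aura onset and treatment start; other recorded deviations. The gap is confined to case 3.

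6. **Pain condition.** Section 13.4.1 tests pain when the aura starts; 10.2 tests it before treatment starts. Suppose moderate headache develops at minute 6 and treatment starts at minute 8. That attack passes 13.4.1 and falls outside the early treatment of 10.2.

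7. **Illustration of unequal omission (assumed inputs).** Suppose there is no true effect. Let q be the share of treated attacks that are barred, p the AMSP2 rate in permitted attacks and b the rate in barred attacks. One arm omits all barred attacks and shows p. The other records all and shows (1 − q)p + qb. The spurious difference is p − [(1 − q)p + qb] = q(p − b).

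| p | b (assumed) | q = 10% | q = 20% | q = 30% |
|---|---|---|---|---|
| 26% | 10% | 1.6 points | 3.2 points | 4.8 points |
| 61% | 30% | 3.1 points | 6.2 points | 9.3 points |

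The values of p are the planning rates in SAP 1.5.1; q and b have no source in the documents. Complete omission in one arm and none in the other is an extreme case. If both arms omit the same share, the difference is zero. The sign depends on which arm omits more.

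**The case against.** The strongest reply is that the rule bars treating as well as recording. Its delay condition concerns being unable to start in time, which is judged before treatment, so it is an attack-level eligibility rule that largely matches the hypothesis in 10.2. The ITT definition then keeps every reported study attack, and the two do not contradict each other. This stands for every compliant participant.

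Case 3 also needs someone to break one half of a sentence and obey the other, while the packaging prompts them to open the app. The Instructions for Use and the case report form content, which are not among the documents, may say more. This limits how often case 3 is likely to occur. It does not supply the missing instruction.

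Two stronger readings are tempting.

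- **That deviating attacks in general are removed before ITT.** They are not; step 5 of the working lists those that remain.
- **That the ITT effect is overstated by several points.** Take the planning rates of 61% and 26%, assume that 10% of treated attacks are late, that all go unrecorded, and that late use does no better than sham. The all-attacks active rate is 0.90 × 61% + 0.10 × 26% = 57.5%, a difference of 31.5 points against 35. At 20% late, the rate is 0.80 × 61% + 0.20 × 26% = 54%, a difference of 28 points. If late use keeps half the effect (43.5%), the gaps are 0.10 × 17.5 = 1.75 and 0.20 × 17.5 = 3.5 points. The sums are right, but the shares and late rates are assumptions. They compare early treatment with all device use, which is dilution across two different questions. They show no bias between arms and no false positive for the hypothesis in 10.2.

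The pain-timing mismatch is probably uncommon in practice. Inclusion criterion 1 requires moderate or severe headache to have begun 10 to 60 minutes after aura onset in more than 75% of past auras, and treatment is to start within 10 minutes.

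**Conclusion.** The concern holds in a limited form. For an attack treated despite the bar, Protocol 13.4.1 instructs the participant not to record it. This works against the ITT rule, the stated use of ITT to study deviations, and the Attack Checklist. Such attacks would be missing from ITT, with number and arm unknown.

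The size cannot be estimated, because the documents do not say how often barred attacks are treated, how often they then go unrecorded, or how they turn out. Between-arm bias requires unequal omission; the figures in the working show only what an extreme imbalance would do under assumed inputs. With equal omission and no true effect there is no spurious difference. The conclusion rests on the literal text of 13.4.1 and on no other participant document overriding it.

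The difference in pain timing between 13.4.1 and 10.2 is a separate inconsistency that the sponsor must reconcile. Nothing here bears on which condition is right.

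**What to change.** - **Recording rule.** Leave the treatment conditions as they are. State in Protocol 13.4.1, the Instructions for Use and the training that every attack in which a study device was used is recorded in the app, whatever the delay or pain level. It enters ITT as a deviation. Both items are already asked at the start, and the ITT definition needs no change.
- **Untreated auras.** Add a one-item app entry for an aura not treated, with the reason, and tabulate these by arm. This covers the selection that occurs even when everyone complies.
- **Device count.** At Site Visit 2, where unused devices are already returned, compute for each participant: five dispensed, minus unused devices returned, minus any used in the Instruction Session, minus recorded attacks. Report the remainder, used-but-unrecorded or unaccounted-for devices, by arm.
- **Pain condition.** Reconcile 13.4.1 with 10.2.

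Cost: a sentence in each participant-facing document, one app item, and one table. The ITT estimate may become less favourable. Recorded late attacks also count toward the four that end Stage 1 (Protocol 10.3.1), so they may displace early-treated attacks. If participants are already enrolled, apply the rule in both arms from a stated date and rely on the device count for the earlier period.
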